4.0 Research Design and Methods

4.1 Type of Study

This is a single-site study that will take place at VA Pittsburgh Healthcare System, Pittsburgh, PA. It is a prospective randomized clinical trial evaluating the two different nerve block injection drugs for TKA and THA, introduced above and described further below. All described RegA techniques strategically avoid GETA and high-dose opioids, and the immediate postoperative complications (from GETA and high-dose opioids) that inhibit full-capacity cognitive function needed to accomplish PT/OT goals during the first 2 days after TKA/THA. Two hundred (200) total patients will be recruited and evaluated for study outcomes pre-TKA/THA (100 for TKA, 100 for THA). Following pre-surgical evaluation, patients will be block-randomized (stratified by [a] TKA vs. THA surgical procedure, [b] age, and [c] presence of diabetes). After surgery, all patients will undergo the same standardized PT/OT best-evidence care plans consistent with current clinical care at our institution. Evaluation of study outcomes will take place during the first two days after surgery, throughout the remainder of the hospital stay (which typically ranges from 2 to 5 days, including discharge day), and during the first two orthopedic post-op follow-up evaluations. The primary outcome is pain at 24 hr after surgery, and exploratory outcomes include physical therapy progress and anesthesia-related symptoms. We will also assess additional metrics of anesthesia and physical therapy success such as range of motion, physical function and performance testing, length of hospital stay, discharge placement, readmission, falls, and other adverse events.

Study Treatment Groups:

Institutional Standard of Care (ISOC)

All patients will receive a standardized bupivacaine spinal anesthetic, consistent with current institutional practice. All patients will receive pre-medications for the prevention of pain, nausea, vomiting, and gastroesophageal reflux, consistent with current institutional practice. All patients will receive intravenous hydration, intravenous antiemetics, and intravenous blood pressure support (e.g., intravenous phenylephrine bolus/infusion) consistent with our current institutional practice. The need for intraoperative blood transfusion will occur based on current institutional practice and collaborative decision-making between the surgical and anesthesia teams, consistent with current institutional practice.

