4.3 Study Visits & Procedures

Study Visits:

The study procedures to be conducted for each subject enrolled in the study are presented in tabular form in Appendix 1 and described in the text that follows. Additional information is provided in the manual of operating procedures.

The study team will attempt to coordinate all of the research questionnaires and physical therapy sessions with the patient's other inpatient and outpatient appointments at VAPHS. However, if this is not possible, the patient will be required to come in for additional visits to complete the research surveys and physical tests at the described study time-points. The total additional time required for the subject participating in this research study is approximately 4-5 hours (not including transportation to and from VAPHS). Patients participation in this study will be approximately 3-4 months and will consist of 1-2

visits prior to surgery, the day of surgery visits (pre- and post- surgery), their in-hospital post-surgery visits and two follow-up visits, scheduled in conjunction with their standard of care ortho scheduled post-surgery visits.

After surgery, all patients will undergo the same standardized PT/OT best-evidence care plans (knee-specific, and hip-specific, respectively) consistent with current clinical care at VA Pittsburgh Healthcare System.

Throughout the study and after the patient signs consent, if the patient is signed up to use the VA MyHealtheVet online tool, communication between the patient and study team can occur using the secure messaging tool offered through MyHealtheVet.

Screening/Baseline Visits

The screening and baseline visit can be completed on the same day, if feasible. No research screening or baseline procedures can be conducted until informed consent is complete.

Baseline assessments will include demographics (including age and weight), smoking status, diabetes status, comorbidity (CIRS: cumulative illness rating scale), completion of research questionnaires, and completion of physical therapy procedures.

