The **primary hypothesis** of an improvement in pain (measured by the SF-MPQ- version 2) 24 hr after surgery during in-hospital recovery comparing plain local anesthetics versus ISOC MMPNA will be tested using a mixed model. This procedure will test for nerve block drug treatment and surgical site (hip versus knee) effects, as well as an interaction between them. Differences in pain levels will also be examined across the study's day-of surgery, 1, 2, 3, and 4 day, and Follow-Up Visit 1 and Follow-Up Visit 2 time points. The secondary aims of short- and long-term physical therapy and rehabilitation-related benefits will also be examined for nerve block drug treatment and surgical site by a mixed model. The tertiary aim to determine differences in opioid-related side effects will use a mixed model. As with other analyses, there will be an examination for nerve block drug treatment and surgical site effects, as well as an interaction between them, along with analyses of the other randomization strata (age, diabetes) as described above.

The **exploratory aims** of physical therapy progress, return-to-home benefits, etc. will be examined using a mixed model. This procedure will test for nerve block type and surgical site effects, as well as an interaction between them. Number of days from the joint replacement procedure to the patient's home discharge will be assessed. Pain responses, as measured by the SF-MPQ – version 2, and use of postoperative opioids with additional measurement by the Opioid-Related Symptom Distress Scale will also be assessed. General health status will be evaluated with the SF-8 and SF-36. Measures of pain, analgesic side-effects, and general health status will be covariates included in the modeling of the effect of MMPNA on return-to-home.

Only after all data are analyzed and results are checked and verified by the biostatisticians will the study be unblinded.

5.2 Adverse Events. For adverse events, we will calculate cumulative probability using survival analysis techniques such as the product-limit estimator. Unlike proportions, product-limit estimators can be applied at various times following randomization, and can take into account when adverse events occur. The six-week incidence (and 95% CI) of individual adverse events by organ system and relatedness to the study will be calculated for each group. We will estimate the incidence of adverse

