9.2 Recording/Reporting requirements

Eliciting adverse event information

Research subjects will be routinely questioned about adverse events throughout their hospital stay and at study visits.

Recording requirements

All observed or volunteered adverse events (serious or non-serious) and abnormal test findings, regardless of study group or suspected causal relationship to the study drug(s) will be recorded in the subjects’ case histories. For all adverse events, sufficient information will be pursued and/or obtained so as to permit 1) an adequate determination of the outcome of the event (i.e., whether the event should be classified as a *serious adverse event*) and; 2) an assessment of the causal relationship between the adverse event and the study drug(s).

Adverse events or abnormal test findings felt to be associated with the study drug(s) will be followed until the event (or its sequelae) or the abnormal test finding resolves or stabilizes at a level acceptable to the Sponsor-Investigator.

Abnormal test findings

An abnormal test finding will be classified as an *adverse event* if one or more of the following criteria are met:

- The test finding is accompanied by clinical symptoms
- The test finding necessitates additional diagnostic evaluation(s) or medical/surgical intervention; including significant additional concomitant drug treatment or other therapy
 - Note: simply repeating a test finding, in the absence of any of the other listed criteria, does not constitute an adverse event.

- The test finding leads to a change in study drug dosing or discontinuation of subject participation in the clinical research study
- The test finding is considered an adverse event by the Sponsor-Investigator of the IND application

Causality and severity assessment

The Sponsor-Investigator of the IND application will promptly review documented adverse events and abnormal test findings to determine 1) if the abnormal test finding should be classified as an adverse event; 2) if there is a reasonable possibility that the adverse event was caused by the study drug(s); and 3) if the adverse event meets the criteria for a *serious adverse event*.

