APPENDIX 1: Study Calendar

	Screening Visit ^a	Baseline Visit	Day of surgery		Post-Op Day 1	Post-Op Day 2	Post-Op Day 3	Post-Op Day 4	Post-Op Day 5	Follow-Up Visit 1 ^d	Follow-Up Visit 2 ^{c, e}
			Pre-Procedure	Post-Procedure							
Clinical Assessments											
Informed Consent	X										
Determine Eligibility	X										
Demographics	X										
Orthopedic & IMPACT evaluation		X									
Crude Sensation in L2-L4 & L4-S3		X			X	X	X	X	X		X
Straight Leg Raise & Range of Motion		X			X	X	X	X	X		X
Functional Independent Measure (FIM)		X			X	X	X	X	X		X
Standing Balance Test		X			X	X	X	X	X		X
Single Leg Balance Test ^g		X									X
Gait Speed		X			X	X	X	X	X		X
Repeated Chair Stand Test		X				X	X	X	X		X
Stair Climbing Time		X									X
Physical Therapy/ Therapeutic Exercises					X	X	X	X	X		
Comorbidity (CIRS)		X									
Interim Changes											X
Discharge Disposition											X
Opioid Consumption					X ^g						
Anesthesia/Study Drugs			X								
Adverse Events		X	X	X	X	X					
Concomitant Medications		X	X	X	X	X					

	Screening Visit	Baseline Visit	Day of surgery		Post-Op Day 1	Post-Op Day 2	Post-Op Day 3	Post-Op Day 4	Post-Op Day 5	Follow-Up Visit 1	Follow-Up Visit 2 ^{c, e}
			Pre-Procedure	Post-procedure							
Questionnaires											
SFMPQ-2 ^b		X	X	X	X	X	X	X	X		X
DVPRS		X	X	X						X	X
DVPRS- in hospital ^b					X	X	X	X	X		
ORSDS ^b		X			X	X	X	X	X		
QOR-15 ^b		X			X	X	X	X	X		X
WOMAC		X									X
SF-8 ^b			X		X	X	X	X	X	X	
SF-36		X									X
Falls Questionnaire		X			X	X	X	X	X		X

a. The screening visit and baseline visit can be completed on the same day.

b. On post-op hospital days and post-op week 6 follow-up visits, these questionnaires will be completed before the subject has their first physical therapy session for the day.

c. If a patient decides to withdraw from the study after having their surgery, or is withdrawn by the study team during or after their surgery, they will be asked to complete Follow-Up Visit 2.

d. Follow-up visit 1 will occur with the patient's already scheduled standard of care follow-up orthopedic visits. Follow-Up Visit 1 may be performed as a phone call if necessary.

e. Follow up visit 2 will be scheduled to coincide with the patient's standard of care follow-up orthopedic visits.

f. Patient must pass the standing balance test first, before the single leg balance test can be attempted.

g. Opioid consumption will stop being collected at the time of the patient's discharge.

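### The Appendix 1 adverse event row stops at post-operative day 2, which conflicts with section 9.2 and cannot support the six-week incidence promised in section 5.2

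*Combined protocol and SAP*

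**What the plan says.** Section 5.2 plans product-limit estimates for adverse events and states that "The six-week incidence (and 95% CI) of individual adverse events by organ system and relatedness to the study will be calculated for each group".

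Section 9.2 describes collection: "Research subjects will be routinely questioned about adverse events throughout their hospital stay and at study visits". It also requires that every adverse event seen by staff or reported by the patient be recorded, whatever the group or suspected cause, and it gives no end date. Events thought to be drug-associated "will be followed until the event (or its sequelae) or the abnormal test finding resolves or stabilizes".

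In Appendix 1, the row "Adverse Events" has marks at baseline, pre-procedure, post-procedure, POD1 and POD2. As extracted, it has none at POD3, POD4, POD5, Follow-Up Visit 1 or Follow-Up Visit 2.

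Section 4.3 says the procedures are "presented in tabular form in Appendix 1 and described in the text that follows", with more detail in a manual of operating procedures that is not part of the documents. It does not say which source prevails if they differ.

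**The concern.** A six-week cumulative incidence needs patients to be asked about new events for six weeks. The calendar is the page that site staff are most likely to work from, and its row ends about two days after surgery. Section 9.2 says otherwise, so two coordinators could both follow the protocol and collect different safety data.

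What is at stake is the by-group safety summary. Section 5.2 itself expects relevant late events: it treats numbness lasting past 72-76 hr from injection as possible nerve damage. An adverse event row that closes at POD2 closes before that point is reached.

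**Working it through.** No power or sample size formula applies. The check counts calendar cells, places the numbness threshold in time, and sets the passages side by side.

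**1. The calendar count (Appendix 1).**
- Visit columns: 11. Adverse Events is marked in 5. Five columns follow POD2, and 0 of them are marked.
- Rows: 20 clinical + 9 questionnaire = 29. Nine have no mark after POD2: consent, eligibility, demographics, orthopedic/IMPACT evaluation, comorbidity, opioid consumption, anesthesia/study drugs, adverse events and concomitant medications. So 29 − 9 = 20 rows keep at least one mark after POD2.
- Follow-Up Visit 1 is marked in 2 rows, both questionnaires (DVPRS and SF-8).

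**2. Are the columns aligned?** Concomitant Medications shows the same five marks as Adverse Events. For that row, the Amendment 6 entry in Appendix 2 confirms in words that collection ends after POD2. This supports the column positions. The log describes no such stop for adverse events.

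**3. The numbness threshold.** Section 4.3 gives the study drug on the day of surgery. With injection at clock hour h of that day (0 < h < 24), POD2 ends 72 − h hours after injection. For example, h = 6 gives 66 hr and h = 18 gives 54 hr (the clock times are examples). The result is always below 72 hr, so the 72-76 hr threshold is never reached inside the marked window.

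**4. What other rows capture after POD2.**
- Crude sensory examination: POD3-5 and Follow-Up Visit 2.
- Falls Questionnaire: POD3-5 and Follow-Up Visit 2.
- Interim Changes: Follow-Up Visit 2.
- Study logs (section 5.2): persistent paresthesiae with pain or weakness.

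Each covers part of late safety. None is a general inquiry that yields events by organ system and relatedness, which the section 5.2 summary needs.

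**5. Consequence under each reading.** Planned group sizes in section 4.1 are 20 + 20 = 40 control and 80 + 80 = 160 MMPNA patients.
- Staff follow 9.2: events are sought at every contact through Follow-Up Visit 2, and the product-limit estimate can be formed with ordinary censoring.
- Staff follow the calendar and patients are censored at POD2: 0 of 40 and 0 of 160 are at risk at day 42, so the six-week incidence is not identified.
- Staff follow the calendar and patients are counted as followed to six weeks: unsolicited late events are missed and the incidence is biased low. Its size depends on how many events arise after POD2, which the documents do not give.

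**The case against.** The strongest reply is that a blank cell does not prove a stop. The Opioid Consumption row also shows a single mark, at POD1, yet its footnote says "Opioid consumption will stop being collected at the time of the" patient's discharge. Either a spanning cell was lost in extraction, or the calendar sometimes uses one mark for continuing collection. The 20 rows with late marks show that ordinary cell-by-cell marks survive; they do not show that a spanning entry would. This stands, and it is why the first step is to look at the original table. The match with Concomitant Medications makes the reading likely but does not settle it.

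A second reply is that section 9.2 already provides both active questioning and recording of volunteered events. This also stands: the plan does not lack late collection in its text. But nothing ranks 9.2 above the calendar. The rule on following drug-associated events to resolution concerns events already recorded, so it does not find new ones.

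Third, section 5.2 expects prolonged numbness to be seen before discharge, where 9.2 questioning applies. That helps only if 9.2 is the source that staff use.

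Three stronger readings are tempting, and the documents do not support them.
- A reader might infer a conflict with section 4.1, which lists "length of hospital stay, discharge placement, readmission, falls, and other adverse events" and evaluates outcomes "during the first two orthopedic post-op follow-up evaluations". That section names metrics and an overall window but sets no adverse event schedule.
- A reader might argue that the published plain-block rates cited in section 5.2 at day 10, 1 month and 6 months require late collection here. Those times belong to one of the plain-block sources. The range used in the section's concluding comparison comes from another, for which no assessment times are given. That comparison also concerns the institution's past data, not this trial's incidence.
- A reader might treat the unstated censoring date as a flaw of equal weight. Censoring at last assessment is the ordinary product-limit default, so this is missing detail only.

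**Conclusion.** The point holds as a conflict between the calendar row and section 9.2, and as a mismatch between that row and the six-week incidence in section 5.2. The size that can be stated is 0 of 5 scheduled contacts marked after POD2. If the calendar is followed and patients are censored there, nobody is at risk at day 42 in either group. No amount of bias is claimed.

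The conclusion rests on two assumptions: that the row in the original table is blank after POD2, and that the unseen manual of operating procedures does not already resolve the difference. If either fails, or if staff follow 9.2, the bias does not arise. It would go too far to infer that the plan omits late adverse event collection altogether, or that the primary analysis is compromised: 9.2 provides for such collection, and pain at 24 hr is measured before the row ends.

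**What to change.** 1. Check the Adverse Events row against the original table.
2. If it is blank after POD2, mark it at POD3-5 (for patients still in hospital), Follow-Up Visit 1 and Follow-Up Visit 2, so that it agrees with 5.2 and 9.2. Record onset date, organ system and relatedness at each. Follow-Up Visit 1 may already be done by telephone.
3. If collection is truly meant to end at POD2, restate section 5.2 as incidence through POD2, make no six-week claim, and bring 9.2 into line.
4. As a minor clarification, say in 5.2 that each patient is censored at the last actual adverse event assessment, and report the number at risk at day 42 by group. Appendix 2 notes that the follow-up visits do not always fall at weeks 2 and 6.

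The cost is a calendar edit, a sentence in 5.2, and a few extra questions at contacts that already take place.

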“Nerve block analgesia” is not necessarily synonymous with “nerve block numbness.” Analgesia is “pain relief,” and pain relief without numbness is thought to promote early physical therapy. Nerve block numbness (even though the numbness is indeed providing pain relief) is expected to delay physical therapy due to lack of muscle strength during numbness. One of the goals of the study’s exploratory aims is to determine if the MMPNA 4-drug combination provides both improved pain relief and improved physical therapy in the days after surgery (when compared with plain bupivacaine).

Anesthesia planning for invasive orthopedic surgery after battlefield-sustained polytrauma above and below the abdomen typically requires general endotracheal anesthesia (GETA) for surgical stabilization of all traumatic injuries. However, based on recent anesthetic innovations, GETA is no longer required for elective TKA/THA, and therefore GETA is not specifically required for one-sided lower-extremity polytrauma. For TKA/THA, the exclusive use of RegA (without GETA) is not only feasible and sufficient, but also comparatively effective via reductions in morbidity and mortality (based on population data).⁽²⁾ GETA has temporary adverse effects on immediate postoperative cognitive function after surgery, and the cognitive risks after multiple episodes of GETA is unknown but is unlikely to be beneficial long term. Eliminating GETA as a confounder of immediate physical therapy / occupational therapy (PT/OT) outcome evaluation now allows for proper evaluation of anesthesiologist physician-directed pain relief, and this study of veteran-specific care has the potential to immediately translate to the care of injured military personnel.

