ISOC MMPNA Block Group (n=80 TKA and 80 THA patients) will receive the ISOC 4-drug MMPNA nerve blocks at the L2-L4 and L4-S3 nerves/plexi. These blocks will be placed before the administration of spinal anesthesia, per our ISOC.

Active Control Block Group (n=20 TKA and 20 THA patients) will receive “active control” nerve blocks comprised of plain bupivacaine. As with the ISOC MMPNA Block Group, these blocks will be placed before the administration of spinal anesthesia, per our ISOC. Again, these blocks will involve the same L2-L4 and L4-S3 nerves/plexi as those for the ISOC MMPNA Block Group.

All study team members will be blinded to the nerve block treatment group/drug the patient receives/received for the described blocks. The only unblinded person regarding the study treatment will be the anesthesia team member who prepares the nerve block injection syringes, based on the randomization envelope assignment. This person who prepares the drug syringes will be otherwise uninvolved with the care of the study patient.

Table 1. Anatomic location of the analgesic nerve blocks used based on TKA versus THA

Basic description of regional anesthesia and analgesia care plan	TKA block details	THA details
Spinal anesthesia, L2-L4 and L4-S3 perineural/plexus single-injection nerve blocks	L2-L4 nerve block entails the femoral nerve in the groin. The L4-S3 nerve block entails the sciatic nerve as it emerges from the sciatic notch deep to the gluteal musculature.	L2-L4 plexus block entails the lumbar plexus within the psoas compartment, 2-3 inches lateral to the lumbar spine midline. The L4-S3 plexus block entails the lumbosacral trunk and parasacral plexus, which lies lateral to the lateral margin of the proximal sacrum. The plexus lies deep to the sacroiliac ligament.

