The tester uses a stopwatch to measure the amount of time the participant is able to stand on one limb. Time commences when the participant raises the foot off the floor. Time ends when the participant either: (1) uses the raised foot (moved it toward or away from the standing limb or touched the floor), (2) moves the weight-bearing foot to maintain his balance (ie, rotated foot on the ground), (3) a maximum of 45 seconds elapses. Three trials are performed in each side and recorded. This exam takes around 6 minutes.

Crude Sensory Examination: Sensory examination is carried out by touching lightly the patient in the specified anatomic distribution of L2-L4 and L4-S3 bilaterally, while the patient has his eyes closed. The patient is asked if the sensation is of equal intensity on both sides (normal), or if one side feels less than the other, or is unable to be felt (diminished or absent). This exam takes around 2 minutes.

Hip, Knee and Ankle Range of Motion: Range of joint movement is measured with a standard goniometer during passive (movement assisted by the tester) and active (without assistance by the tester) movements. Range of motion is tested with the subject lying in supine on the hospital bed or examination table. This is performed on both sides and recorded in degrees. Range of motion takes approximately 5 minutes.

Straight Leg Raise: The subject is asked to raise one lower extremity from the hospital bed up to approximately 45 degrees from the horizontal without bending the knee. The test is performed in both sides, and is recorded as “Yes” if the subject is able to raise the lower extremity higher than 20 degrees from the horizontal, or “No” if unable to lift the leg at that level. During this test the examiner also observes the presence of a knee extension lag, which is defined as a knee flexion (lag) equal or greater than 5 degrees during the straight leg raise. It takes approximately 3 minutes for the straight leg raise activity.

Stair climbing time: This test measures the time the subject takes to go up a flight of stairs. Subjects are instructed to use the handrail for safety purposes. The tester uses a stop watch to record time. It takes approximately 5 minutes for this test.

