events in both groups with specific focus on those deemed definitely, probably, or possibly related to interventions. For adverse events, clinical judgments will be considered more important than statistical testing.

Prolonged analgesic duration Sustained / prolonged nerve block analgesia, which we hypothesize to be true in our ISOC MMPNA Group, is NOT a complication that warrants medical attention as a possible complication. That this is NOT a complication is especially true in the context of perineural analgesia being designed to facilitate postoperative physical therapy in the first few days after surgery. In our evaluation of analgesic duration, a central question for patients will be “when did you first take a prescription opioid pain pill, but it did not help?” Another (indicating even further pain severity) is “when did you first get an intravenous opioid dose, but it did not help? The dates and times of these events are important and clinically practical indicators that the perineural analgesia is no longer effective. This is because postoperative oral multimodal analgesia is designed to (i) supplement the lingering analgesic effects of the nerve block, and (ii) delay the onset of the peak pain score encountered after the perineural analgesia “wears off.” “Peak rebound pain scores” may not necessarily entail excruciating pain. But if excruciating pain is encountered despite oral and intravenous opioids, then it is likely that there is no persisting perineural analgesia. Conceptually, when combining CBD with bupivacaine (in the ISOC MMPNA group), the bupivacaine provides short-lived numbness and analgesia (e.g., a theoretical 12-16 hr), but the CBD likely sustains perineural analgesia without numbness (e.g., for an additional theoretical 24 hr). The study is designed to accurately capture these two separate phases of analgesia, since we do not have preliminary data on these separate phenomena (analgesia with numbness, then analgesia without numbness).

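### The protocol claims to capture analgesia with and without numbness as separate phases, but nothing in the documents records when numbness ends, so each patient's phase lengths can only be bounded

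*Combined protocol and SAP*

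**What the plan says.** Section 5.2 (paragraph on prolonged analgesic duration) describes two phases in the 4-drug arm. First, "the bupivacaine provides short-lived numbness and analgesia (e.g., a theoretical 12-16 hr"; then "the CBD likely sustains perineural analgesia without numbness (e.g., for an additional theoretical 24 hr". It adds "The study is designed to accurately capture these two separate phases of analgesia", and gives the lack of preliminary data on either phase as the reason.

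The items that bear on this are:

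- **Numbness.** Section 4.3 describes a light-touch comparison of the two legs: "Sensory examination is carried out by touching lightly the patient in the specified anatomic distribution of L2-L4 and L4-S3 bilaterally". The result is the state at that moment: "The patient is asked if the sensation is of equal intensity on both sides (normal", otherwise diminished or absent. The Appendix 1 row "Crude Sensation in L2-L4 & L4-S3" is marked at Baseline, Post-Op Days 1-5 and Follow-Up Visit 2. Both day-of-surgery columns are blank.
- **Time zero.** Section 4.1: "These blocks will be placed before the administration of spinal anesthesia, per our ISOC".
- **Timed items.** Section 5.2 asks when an oral opioid, and when an intravenous opioid, was first taken without effect. Section 4.4 defines block duration from placement to peak DVPRS score with movement.
- **Analysis.** The outcome list in section 5.1 does not include the sensory examination, and no analysis of either phase is given.

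**The concern.** Separating the two phases requires one quantity, the time numbness ends. It closes the first phase and opens the second. Every timed item in the plan marks a different event, the end of pain relief as a whole. The only item that looks at numbness has no time of change attached and is not done in the hours when the protocol's own figures say the change happens.

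Section 2.1 explains why numbness matters apart from analgesia: it is expected to hold back physical therapy through loss of muscle strength. Section 7.3 says it is not known whether the 4-drug block prolongs pain relief or unwanted numbness. A reader of the results would look to this trial for the length of each phase. A day-1 exam that is mostly normal in both arms could then be read as showing equal numbness duration when it shows only that most offsets came earlier.

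**Working it through.** **1. The protocol's own totals.** First plus second phase: 12 + 24 = 36 h and 16 + 24 = 40 h. These agree with the roughly 36 h in section 2.1 and the 40 h mean in section 5.6, so the two-phase description is internally consistent.

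**2. When the first exam falls.** No clock time is stated, so this is an assumption. Hours from block to day-1 exam = 24 - block clock time + exam clock time. Blocks at 07:00-13:00 and exams at 07:00-12:00 give 24 - 13 + 7 = 18 h up to 24 - 7 + 12 = 29 h. The exam comes at 16 h or earlier only for late blocks with early exams (15:00 and 07:00: 16 h; 16:00 and 07:00: 15 h; 16:00 and 08:00: 16 h). I use 18-28 h below.

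**3. Share of end-times before the first exam.** If 12-16 h were a hard range, the share would be 100% at any exam from 18 h on. Allowing spread, take numbness as normal with mean m and SD m/2. Section 5.6 uses that ratio for analgesic duration; applying it to numbness is an assumption. Share = Φ((t - m)/(m/2)):

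| m (SD) | t = 18 h | 20 h | 24 h | 28 h |
|---|---|---|---|---|
| 12 (6) | 84% | 91% | 98% | 99.6% |
| 14 (7) | 72% | 80% | 92% | 98% |
| 16 (8) | 60% | 69% | 84% | 93% |

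For m = 14-16 h the range is about 60-98%. With m = 12 h it reaches nearly 100%.

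**4. What is then known about a patient.** With total analgesia T and a normal first exam at t, the first phase lies in (0, t] and the second in [T - t, T). Both intervals are t hours wide.

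- t = 24, T = 36: first phase at most 24 h, second in [12, 36).
- t = 24, T = 40: first phase at most 24 h, second in [16, 40).
- t = 18, T = 36: first phase at most 18 h, second in [18, 36).

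The width of 18-28 h compares with an expected second phase of about 24 h.

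**5. If numbness lasts longer.** Section 5.2 also applies a mean of 48 h and SD of 14 h to numbness, as a conservative bound for a safety check. Then 1 - Φ((24 - 48)/14) = 96% are still numb at 24 h, and the end falls between two daily exams, a gap of about 24 h. That holds only while the patient is in hospital. Section 4.1 gives a usual stay of 2-5 days, and the next exam after discharge is at Follow-Up Visit 2.

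**6. What the day-1 exam can still show.** Suppose mean numbness is 10 h (SD 5) in one arm and 18 h (SD 9) in the other. The shares still numb at 20, 24 and 28 h are 2.3%, 0.3% and 0.02% against 41%, 25% and 13%. Power of a two-sided 5% Fisher test is the sum of the binomial probabilities of all result pairs with p < 0.05. With 160 against 40 patients it is above 99%, above 99% and about 95%. Within one procedure (80 against 20) it is about 99%, 90% and 11%. For a smaller shift, 14 h (SD 7; 20%, 8% and 2% numb) to 18 h (SD 9), pooled power is about 73%, 71% and 50%.

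**The case against.** Four points deserve weight.

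- A reader might infer that the trial cannot detect prolonged numbness at all. Step 6 does not support that: pooled over procedures, a shift from 10 to 18 h would very probably show in the proportion numb on day 1. What is lost is the duration, not all sensitivity to a difference. Day 1 is also when scheduled therapy begins, so being numb or not at that point is itself relevant to therapy.
- A reader might infer that numbness will be over, and the exam normal in nearly everyone, by day 1. The documents do not establish that. The 12-16 h is labelled theoretical, no exam hour is given, and the 48 h bound points the other way. But step 5 shows that longer numbness still leaves an uncertainty of about a day.
- Numbness duration is not a named primary, secondary or tertiary outcome, and no planned analysis depends on it. This limits the weight of the point. The protocol nonetheless claims the property in plain terms.
- The two opioid questions are not presented as an exhaustive list, and the manual of operating procedures and data collection forms are not among the documents. One of them may already time the return of feeling. If so, the protocol and analysis plan should say so and define the variable.

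An early postoperative sensory check could also be confounded by the spinal anesthetic. That favors asking the patient for a time over simply adding a day-of-surgery exam.

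**Conclusion.** The point stands in this form: as documented, the design bounds the two phases but does not measure them. The interval for an individual is about 18-28 h wide if numbness ends before the first exam and about 24 h wide if it ends between daily exams, against an expected second phase of about 24 h. The 60-98% share of end-times before the first exam rests on three assumptions: mean numbness of 14-16 h, an SD of half the mean, and an exam 18-28 h after injection. The absence of a recorded end-time rests on none of them, only on the documents being complete on this point.

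Total analgesic duration remains obtainable. The 24-hour pain endpoint and the check for numbness beyond 72-76 h are unaffected. This is an exploratory matter, but the protocol claims it explicitly and it is cheap to put right.

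**What to change.** Add one item beside the opioid questions on the existing day 1-5 forms: *At what date and time did normal feeling return in the operated leg?*, with *not yet* as an option. In the analysis plan:

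- define numbness duration as block placement to that time;
- check each answer against the last abnormal and first normal exam;
- analyze the duration as interval-censored, and state how patients still numb at discharge are handled;
- define the second phase as end of analgesia minus end of numbness, naming which timed item marks the end of analgesia.

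The cost is one question and a paragraph of analysis wording, with no new visit or assessor. The drawback is recall error for changes that happen overnight, which the exam results only partly limit.

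If the question is not added, withdraw the claim of accurate capture. Report the proportion numb at each daily exam by arm, with the time since block, and state that no difference on day 1 is not evidence of equal numbness duration.
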